9.3 Procedures for Reporting and Recording of Serious Adverse Events

Reporting of Serious Adverse Events

The Investigator must report all SAEs/SADEs, DDs and device incidents that could have led to a serious adverse device effect to the Sponsor Safety Officer not later than within 24 hours after the knowledge of the event. The information must be sent by fax by filling in the SAE forms or DD or device incidents form.

Day 0 is the day that the Sponsor receives a notification report from an Investigator. Any SAE/SADE/device incident is to be tracked and assessed by the Sponsor. The Sponsor will report any SAE/SADE/device incident to the relevant IEC as required by local requirements of the committee and to the Competent Authority. Any SAE/SADE/device incident is to be tracked and assessed by the Sponsor. Any SAE/SADE/device incident that might have led to a SAE if suitable action had not been taken or intervention had not been made or if circumstances had been less fortunate will be reported to the Competent Authority.

The contact for reporting is:

[name]

mobile [contact]

mail: [contact]

Reporting of Serious Adverse Events to National Competent Authority

The Sponsor commits to report the following events to the National Competent Authority:

- a) Any SAE;
- b) Any DD or device incident that might have led to a SAE if suitable action had not been taken or intervention had not been made or if circumstances had been less fortunate (near incident);
- c) New findings/updates in relation an already reported event.

The time-line for reporting reportable events is as follows:

- a) Investigator to Sponsor:
 - not later than within 3 calendar days after the occurrence of the event
- b) Sponsor to National Competent Authority
 - Serious public health threat: immediately (without any delay that could not be justified) but not later than 2 calendar days after awareness by the Manifacturer of this threat;
 - Death or unanticipated serious deteration in state of health: immediately (without any delay that could not be justified) after the Manufacturer established a link between the device and the event but not later than 10 elapsed calendar days following the date of awareness of the event;
 - Others: immediately (without any delay that could not be justified) after the Manufacturer established a link between the device and the event but not later than 30 elapsed calendar days following the date of awareness of the event;

9.4 Follow-up of adverse events

Complete and accurate data on all AEs experienced for the duration of the reporting period will be reported on an ongoing basis in the AE forms of the CRF.

It is important that each AE report include a description of the event, its expectedness, whether it is considered serious, its duration (onset and resolution dates), its intensity, its relationship to the medical device, any other potential causality factors, any action taken and its outcome.

Note: After completion of the investigation the Sponsor will continue to have an obligation to report serious and treatment-related AEs affecting the investigation subjects.

9.5 Follow-up of SAEs/SADEs/device incidents

- Reporting of SAEs/SADEs/device incidences from the investigator site begins from signing of informed consent and ends at the last investigation visit/last follow-up contact.
- All new SAEs/SADEs/device incidences occurring beyond this time frame and coming to the attention of the investigator must be recorded only if they are considered (in the opinion of the investigator) causally-related to the investigational device. Thus, only SAEs/SADEs/device incidences related to the investigational device will be followed after Visit 4, until resolution, stabilization or subject loss at follow-up.
- Reports of SAEs/SADEs/device incidences occurred during the investigation or after the site closure should be reported directly from the Investigator to the Sponsor Safety Contact.
- All SAEs/SADEs/device incidences should be followed-up in order to elucidate as completely and practical as possible their nature and/or causality. The follow-up information should be submitted until resolution of all queries, clinical recovery is complete, laboratory results have returned to normal, until progression has been stabilized or until the subject is lost to follow-up. Follow-up may therefore continue until after the subject has left the investigation.
- In case of death, a comprehensive narrative report of the case should be prepared by the Investigator and sent to the Sponsor Safety Contact by fax together with the SAE form, retaining a copy on site with the CRF.

• If an autopsy is performed, copy of autopsy report should be actively sought by the Investigator and sent to the Sponsor Safety Contact as soon as available, retaining a copy on site with the CRF.

9.6 Pregnancy

- In case of accidental pregnancy, the subject will be immediately withdrawn from the investigation;
- If the pregnancy meets the criteria for immediate classification of a SAE (e.g. spontaneous or therapeutic abortion, stillbirth, neonatal death, congenital anomaly, birth defect) the Investigator must follow the procedure for reporting SAEs (see Section 9.3).

10. DATA MANAGEMENT AND STATISTICAL ANALYSIS

Data management and statistical analysis will be performed under the responsibility of the Sponsor.

10.1 Data management

10.1.1 Case report form (CRF)

The data generated in this investigation will be recorded at the investigational site by the appointed investigation personnel on an investigation-specific CRF.

A paper CRF will be designed to record all the protocol-required information to be reported to the sponsor. The main purpose of the CRF is to obtain data required by the clinical investigation protocol in a complete, accurate, legible, and timely manner.

All subjects' data, recorded in the CRF by the Investigator and/or his/her designee, will have to find source in the source documents (e.g., subject's medical records).

The CRF should be filled-in during or immediately after the conclusion of each visit, preferably within 24 hours but no later than five working days after the visit.

No blank sections or unanswered questions should appear in the CRF: in the case that the requested information cannot be provided, the statement "NAV" (not available) or "ND" (not detected) should apply specifying the reason or "NA" (not applicable) if not pertinent; in the section "notes/observations the statement "none" or "NOR" (nothing of relevance) or a cross line should apply when there is no need to provide further information.

The completion of the CRFs will be done using an indelible writing possibly in black colour (use a ball pen, not a fountain pen). Possible changes or additions to data already reported in the CRF should be performed using an indelible writing, possibly in black colour, dated and initialled by the person who performs changes. The reason of change/addition should be explained. In the case of correction, the original data should not be modified but erossed in order that the original version remains legible and verifiable. In no circumstances erasures or masks of the original data with masking fluids should appear.

The forms of the CRFs will be produced in a self-copying paper in thrice copy, one white (original, to be withdrawn by the sponsor) and two coloured copies (one to be sent to the statistician and another to be stored in the site documentation).

In the event that the CRF section dedicated to the recording of adverse events is not sufficient for the completion of recordings, a photocopy of the blank CRF can be used: in this case the original copy will be withdrawn by the monitor and 2 photocopy will be attached and punched to the corresponding CRF.

In exceptional, motivated and documented cases, the use of paper photocopied CRFs will be allowed, which will be managed as indicated in the paragraph above.

The Investigator or designee is responsible for ensuring that the data collected in the course of this investigation is accurate and documented appropriately on all applicable forms. They will then be processed, evaluated, and stored in pseudo-anonymous form in accordance with applicable data protection regulations. The Investigator must ensure that the CRFs and any other associated documents forwarded to the Sponsor or its designated organization contain no mention of any subject names or identifier.

Data reported on the CRF are confidential and have to be consistent with the source documents. The Investigator must ensure the accuracy, the completeness and the consistency of the data entered in the CRF.

The names of personnel authorized to handling the CRFs are to be given to the assigned investigation monitor before investigation initiation.

The CRFs will be archived by the investigator, as part of the essential clinical investigation documents, in a locked storage facility of the investigational study site. The data registered on the CRFs of all included subjects will be stored in a suitable database properly designed under the responsibility of th Sponsor.

Double data entry will be performed manually by the Data Entry Operators in the database. Data validation checks will be performed electronically/manually for internal consistency and completeness.

Queries generated from data entry and validation checks are issued by the Data Cleaning Operator or Data Manager according to the plan of controls previously prepared and will be referred to the Investigator.

After queries and quality checks and once the investigation database is considered cleaned, a data review meeting will be held before database lock in order to assign the subjects to each of the analysis sets according to the specified definitions.

Afterwards the database can be locked the planned statistical analysis will be performed.

10.2 Statistical analysis

All statistical analyses will be performed using Stata version 16.1. The software used to perform the statistical analysis, as well as the data management activities, is fully validated.

The following describes the statistical analysis as it is foreseen at the time of planning the investigation. A detailed statistical analysis plan (SAP) will be issued before database lock. The contents of the SAP will include the investigation's objectives, type of primary analysis, clear specification of all primary and secondary endpoints, full and detailed descriptions of the statistical methods for data analysis and will address special issues such as definition of major protocol violators, definition of subjects and data included in or excluded from each analysis, and exploratory analyses.

The plan will be reviewed and may be updated before the start of the statistical analysis, which will start only at the end of data management activities and after the description and discussion of protocol deviations by the clinical team during a data review meeting. During the meeting subjects will be confirmed in the respective analysis populations. Subjects' exclusion from each of the analysis populations will be documented and justified in a Data Review Report.

All data obtained in this investigation and documented in the CRFs will be listed and summarized with statistics or frequency tables as appropriate.

Statistical testing will be two-sided. All p-values will be rounded to the first two significant (different from zero) decimal digits, or to one significant digit if lower than 0.001. Statistical significance will be declared if the p-value will be less than 0.05. Two-sided 95% confidence intervals (CI) for outcome variables will be calculated, unless otherwise specified.

For quantitative safety and performance variables, analysis within treatments sequence will also be presented.

10.2.1 Sample size

A sample size of 52 subjects achieves 81% power to detect a mean of paired differences of 1.0 with an estimated standard deviation of differences of 2.5 and with a significance level (alpha) of 0.05 using a two-sided paired t-test.

A maximum number of 55 subjects may be recruited to account for a rate of non-evaluable subjects of about 5%

10.2.2 Populations for analysis

The following populations are defined for this investigation:

- Enrolled population: all subjects who sign the informed consent and are enrolled in the investigation after evaluation of all inclusion and exclusion criteria;
- Intention-to-treat (ITT) population: all subjects who received almost one of the investigational devices;
- Modified ITT (mITT) population: all subjects of the ITT population who have at least one valid post-treatment record per treatment;
- Per-Protocol (PP) population: all subjects of the mITT population who also meet all inclusion/exclusion criteria and who do not have any major protocol deviation (e.g. use of forbidden concomitant medications, inadequate or poor compliance to investigation procedures, etc.).
- Safety population: all subjects of the ITT population who receive at least one application of the investigational medical devices;

The analysis of safety endpoints will be performed in the safety population. The analysis of performance endpoints will be conducted in the mITT population and will be repeated in the PP population. The results obtained in the PP population will be seen as confirmative of those observed in the mITT population.

10.2.3 Missing data

Not applicable. No procedures for replacement of missing values will be used.

10.2.4 Coding Dictionaries

Adverse events (AEs), past and concomitant diseases will be coded using the Medical Dictionary for Regulatory Activities (MedDRA). All verbatim terms will be assigned to a Preferred Term (PT) and will be classified by primary System Organ Class (SOC) according to the most recent MedDRA thesaurus version.

Previous and concomitant medications will be coded using the WHO-DRL Dictionary version 2015 or higher and classified according to 3rd level ATC level subgroup and generic name.

10.2.5 Statistical methods

Descriptive Statistics:

Descriptive statistics will be provided in summary tables by treatment group according to the type of variable.

Continuous variables will be summarized by number of observations, mean and standard deviation, median, minimum, and maximum. Categorical variables will be summarized using counts of subjects and percentages.

All data collected will be presented in the listings.

Subject accountability:

Disposition of subjects, subject status and subjects excluded from different analysis sets will be summarized.

Baseline characteristics:

Demographic and baseline characteristics will be summarized by means of descriptive statistics. No formal statistical tests will be performed to verify the homogeneity of the sequence groups at baseline visit (intra-subjects study).

Performance endpoints

Primary performance endpoint will be the mean pain score experienced by the subject in the first hour after each treatment. The pain measurement will be obtained from the VAS scores. Based on these VAS scores, the area under the curve from treatment until 1 hour after will be calculated and this area under the curve will be divided by time. This resulted in a mean VAS score that will be compared between treatment with a paired t-test.

For secondary endpoint a two-sided Wilcoxon signed-rank test will be done.

Safety endpoints

AEs which occurred before and those which started after the application of the investigational device (treatment-emergent AEs, TEAEs) will be presented separately.

All AEs will be tabulated by System Organ Class (SOC) and Preferred Term (PT) after medical coding using the most recent MedDRA thesaurus version. The primary SOC and the PT will be used for the analysis of the frequency distribution in the two groups.

The number of TEAEs (i.e. AEs started after the start of treatment), treatment-emergent SAEs, TEAEs related to the medical device under investigation, treatment-emergent SAEs related to the medical device, and the number and proportion (with exact 95% CI) of subjects with at least one TEAE, treatment-emergent SAE, TEAE related to the medical device and treatment-emergent SAEs related to the medical device will be presented by treatment group.

The incidence of TEAEs in the two treatment groups will be compared by means of McNemar test.

Risk ratios and odds ratios with 95% CIs, Fisher's exact test and logistic regression will be considered to compare proportions between treatment groups.

The results of changes from baseline in vital signs (blood pressure and heart rate) will be presented as descriptive statistics.

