5.2 Dosage and administration

The investigational medical devices must be administered only to subjects selected for taking part in the investigation according to the protocol.

Duration of treatment

Single admnistration of each device (one on right side and the other on the left side of the face).

Dosage and mode of treatment

- study devices will be administered using linear threading, multiple punctate pools, and/or fanlike injection technique. The technique of injectiom and the depth of injection will be at the discretion of the Treating Investigator; however, for a given subject, both devices will be injected at the same depth and with the same technique.
- in all subjects the first injection will be done in the right side of the face, the second in the left side.
- doses: the minimum amount must be at least 0.5 ml per side, the maximum 2 ml per side, per each implant. The Treating Investigator will decide the dose to obtain the optimal correction of defect per each patient implant.

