5.4 Treatment code

A computer-generated randomization list (specifying the type of medical devices to be injected in the right and the left side of the face) will be available.

Each subject included in the investigation will be coded by the Investigator through a 2-digit progressive *Screening number* as they present themselves for the investigation at the screening visit (Visit 1), starting from code 01 preceded by the letter "S" (first subject enrolled: code S01).

If a subject discontinues from the investigation, the screening number will not be re-used, and the subject will not be allowed to re-enter the investigation.

Eligibility confirmed, a randomization number will be done starting from 01 (first subject randomized: code 01).

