 - 12. Replace the used siringe in the box (without needle);
 - 13. Store in a safe place for future check.

Repeat the procedure for the LEFT side of the face.

Warnings: Do not use product after the expiry date. Do not use the product if the primary package is not intact or damaged. Do not use the product if it does not appear to be in normal condition. The siringes are disposable and CANNOT BE RESTERILISED; once the package has been opened, the material must be used immediately. Do not mix the medical devices with other substances. Do not place in contact the devices with quaternary ammonium salts as benzalkonium chloride. Do not inject any type of drug into the gel.

- Pain assessment. After implantation, participants will remain in a medical room for at least 60 minutes to be assessed for possible adverse events and for the pain. Pain will be assessed by the Blind Evaluator immediately (within 1 min) after the last injection and later after 15-30-45-60 min. by means of a 100-mm Visual Analogic Scale (VAS) (see paragraph 7), separately for each side.
- Adverse events will be monitored throughout the duration of the study (from obtainment of Informed consent to end of the study) and recorded in the subject's medical records and in the appropriate section of the CRF;
- An appointment will be taken for the next visit, scheduled after 2 weeks (\pm 2 days).

Visit 2 (week 2 ± 2 days): follow-up visit

The following assessments and procedures will be performed during Visit 2:

- All concomitant medications being taken by the subject will be checked and, in case of changes from the previous visit, will be recorded in the subject's medical records and in the appropriate section of the CRF;
- Vital signs (blood pressure and heart rate) will be measured and recorded;
- The occurrence of adverse events from the previous visit will be checked and (if any) and recorded in the subject's medical records and in the appropriate section of the CRF;
- The GAIS scale will be admnistered;
- The digital photo will be done;
- An appointment will be taken for the next visit, scheduled after 12 weeks from Visit 1.

Visit 3 (week 12 ± 10 days): follow-up visit

The following assessments and procedures will be performed during Visit 3:

- All concomitant medications being taken by the subject will be checked and, in case of changes from the previous visit, will be recorded in the subject's medical records and in the appropriate section of the CRF;

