13.5 Protocol amendment(s)

Neither the Investigator nor the Sponsor will modify or alter this protocol without first obtaining the agreement of the other part. A new approval from the IEC must be obtained before implementation of any substantial amendment, except when it is necessary to eliminate apparent immediate hazard to the subject.

All agreed substantial protocol amendments must be clearly recorded, signed and dated by the Sponsor and the Principal Investigator.

Any non-substantial amendment has to be signed by the responsible Sponsor. The original document will be filed in the investigation Master File. In trials conducted in the European Union (EU), there is no need to notify non-substantial/minor amendments to IEC or Competent Authorities, but all minor amendments should be recorded and kept available for any request for inspections at the investigational site or the Sponsor premises and should be contained in the documentation when it is subsequently submitted, for example in the subsequent notification of a substantial amendment.

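### The primary paired t-test omits side/order, the factor to which the device is randomised; adding a sequence term would be a cheap gain in precision to a valid test (minor).

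*Combined protocol and SAP*

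**What the plan says.** Section 5.2 fixes the order of injection for all subjects: the right side comes first, then "side of the face, the second in the left side". Section 5.4 describes a computer-generated list "specifying the type of medical devices to be injected in the right and the left side of the face". It gives neither an allocation ratio nor blocking.

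Section 10.2.5 forms a mean VAS per side (area under the curve over the first hour, divided by time) and continues: "This resulted in a mean VAS score that will be compared between treatment with a paired t-test". There is no side, order or sequence term. Section 10.2.1 bases the power on the same paired t-test.

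The plan does know about sequence. Section 10.2 says that for quantitative variables "analysis within treatments sequence will also be presented". That is an additional presentation and leaves the primary estimate, CI and p-value as they are. Section 10.2 also promises a detailed SAP before database lock.

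The Protocol Summary describes the paired t-test as a comparison between sequences, and the McNemar test as one between sequence groups, where section 10.2.5 refers to treatments. This is a wording slip; the intended HAL-versus-HA comparison is not in doubt.

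**The concern.** If the same device hurts more (or less) on the right/first side than on the left/second, the HAL-minus-HA difference is raised in one sequence and lowered by the same amount in the other. Under equal allocation this cancels in the mean but stays in the SD of the differences, so the CI is wider than the design requires. If the two sequences end up unequal in size, the effect no longer cancels fully and the estimate shifts by chance. A term for a factor that is already recorded removes both.

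The documents give no size for such an effect, but they give one reason why it may not be zero. Section 6.1 says "Pain will be assessed by the Blind Evaluator immediately (within 1 min) after the last injection". If that means the last injection overall, it is on the left in every subject, and the right side is then scored later after its own injection. Section 1.2 says the anaesthetic effect declines during the first hour. Other passages (sections 7 and 10.2.5) read as if the clock runs separately for each side. These timing passages need to be reconciled in any case. That is a separate matter, and a sequence term would not settle it.

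**Working it through.** **Inputs from the plan (section 10.2.1).** n = 52, mean paired difference 1.0, "estimated standard deviation of differences of 2.5", two-sided alpha 0.05, stated power 81%.

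**Inputs assumed.** A right-minus-left difference for the same device, δ, of 0.25 to 2.0 in the units of the planned 1.0. Sequence split: 26/26, a simple 1:1 list (average over Binomial(52, 0.5)), or 31/21.

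**The plan's own figure.** Noncentrality = (1.0/2.5)·√52 = 2.884. With 51 df, power is 80.78%, which agrees with the stated 81%.

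**Model.** d = θ + δ·s + e, where d is a subject's HAL-minus-HA mean VAS and s = +1 if HAL is on the right, −1 otherwise.
- Planned test: one-sample t on d, 51 df. At 26/26 the variance of d is SD(e)² + δ².
- With the term: the mean of the two sequence means, variance SD(e)²/4·(1/n1 + 1/n2), 50 df.

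**Main case.** 2.5 is read literally as the total SD of differences, so SD(e) = √(6.25 − δ²). The equivalent n is the number the planned test would need for the same CI width: 52·6.25/(6.25 − δ²). Split 26/26:

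| δ | SD(e) | Mean CI width, planned → with term | Narrower by | Power, planned → with term | Equivalent n |
|---|---|---|---|---|---|
| 0.25 | 2.487 | 1.385 → 1.379 | 0.5% | 80.9% → 81.1% | 53 |
| 0.5 | 2.449 | 1.386 → 1.358 | 2.0% | 81.2% → 82.3% | 54 |
| 1.0 | 2.291 | 1.388 → 1.270 | 8.5% | 82.7% → 87.0% | 62 |
| 1.5 | 2.000 | 1.391 → 1.109 | 20.3% | 85.8% → 94.2% | 81 |
| 2.0 | 1.500 | 1.397 → 0.831 | 40.5% | 92.0% → 99.7% | 144 |

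**Simple list.** Power of the planned test is 80.8% throughout. With the term it is 80.4%, 81.5%, 86.3%, 93.8% and 99.7% for δ = 0.25, 0.5, 1.0, 1.5 and 2.0.

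**Cost when δ = 0.** Power goes from 80.78% to 80.75% at 26/26, and to 79.97% on average with a simple list. Break-even on mean CI width is at δ = 0.07 with 26/26 and δ = 0.36 with a simple list.

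**Type I error of the planned test.** At 26/26 it is conservative: 4.89%, 4.55%, 3.27%, 1.45% and 0.11% across the five values of δ. Averaged over a simple list it is 5.0%. Given a 31/21 split it is 5.1%, 5.4%, 6.5%, 7.9% and 7.7%. With the term it is 5.0% throughout.

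**Chance shift at 31/21.** δ·(31 − 21)/52 = 0.05, 0.10, 0.19, 0.29 and 0.38. A simple list gives a split at least this uneven with probability 0.21.

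**Alternative reading.** If 2.5 were the within-sequence SD, power of the planned test at 26/26 would be 80.5%, 79.7%, 76.2%, 70.4% and 62.0%, against 80.75% with the term.

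**The case against.** The planned test is valid, and the sample size was calculated for exactly that test. Under the literal reading of section 10.2.1, its power is 80.8% or more at every assumed side effect, whether the split is 26/26 or the list is simple, so the plan's own target is met. It falls short only if 2.5 is re-read as a within-sequence SD, which section 10.2.1 does not say.

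The size of the effect is wholly assumed, and the large gains come from large values. Effects of 1.0, 1.5 and 2.0 would mean that side/order explains 16%, 36% and 64% of the variance of the differences (δ²/6.25), and 2.0 is twice the planned treatment effect. At 0.5 or below the gain is small, and with a simple list the term loses a little precision below about 0.36. The one reason in the documents for a non-zero effect rests on ambiguous timing wording; if the clock runs per side, that reason falls away. A marked effect would also be visible in the planned within-sequence presentation.

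All of this stands, and it limits the point to a minor one. It does not remove it. The within-sequence presentation does not adjust the primary CI. The largest average loss found is under one power point, against a gain of about four to six points at an assumed effect of 1.0.

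**Conclusion.** The point holds as a minor one. The primary analysis leaves out the factor to which the device is randomised, and a sequence term would be a low-cost improvement to a test that is already valid. In the main case the gain ranges from negligible (CI 0.5% narrower at an assumed side effect of 0.25) through 2.0% at 0.5 to 8.5% at 1.0; the larger figures need large assumed effects. The term also removes the chance shift from unequal sequences, for example 0.19 at a 31/21 split with an effect of 1.0.

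The conclusion that the planned test is valid rests on 1:1 allocation, which the documents do not state. The term handles an additive side/order effect only. It would not repair unequal elapsed times or an effect of order that differs between the devices.

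**What to change.** In the SAP promised before database lock, or in section 10.2.5, prespecify the primary analysis as a linear model of each subject's HAL-minus-HA mean VAS on sequence, coded ±0.5. The intercept and its 95% CI are then the treatment effect. Keep the plain paired t-test as a sensitivity analysis. Make the choice before the data are analysed, so that it cannot depend on the side effect observed.

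Consequential edits: add a clause in section 10.2.1 noting that the power was calculated for the unadjusted paired t-test, and change the two sequence wordings in the Protocol Summary to treatment, in line with section 10.2.5.

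The cost is one degree of freedom (80.78% to 80.75% power at 26/26; about 0.8 points on average with a simple list, if there is no side effect) and a few lines of text. No new data or procedures are needed. If the sponsor classes the change of primary model as substantial, section 13.5 applies: "A new approval from the IEC must be obtained before implementation of any substantial amendment".
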